If at any time U/S shows more than 6 follicles with diameters ≥ 18 mm or E2 reaches $\geq 3,000$ pg/ml, do not give hCG and do not inseminate. EXIT TREATMENT CYCLE AND SKIP NEXT CYCLE. RE-EVALUATE BEFORE CONTINUING TREATMENT.

be performed 36-40 hours after hCG administration. Couples will be advised to abstain from intercourse for 72 hours following the insemination in order to insure that any conceptions occurring in that cycle are actually the result of the treatment.

Women who develop only one follicle measuring ≥ 18 mm by cycle day 15 (i.e., after 12 days of hMG stimulation) will receive hCG on day 15 and undergo insemination as above, but will commence the next cycle (unless pregnancy occurs) with 4 amps per day of hMG. In all other respects they will follow the above protocol for hMG administration and monitoring.

Women who show no follicle development by cycle day 15 will not receive hCG or insemination, but will commence the next cycle with 4 amps per day of hMG. If criteria for hCG administration are not reached on this high-dose hMG regimen, no further attempts at ovarian stimulation will be provided as part of the study.

At any time, if more than 6 follicles measuring ≥ 18 mm (range 16.2-19.8 mm) are seen by U/S or if E_2 reaches $\geq 3,000$ pg/ml (range 2700-3300 pg/ml), no hCG will be given and no insemination will be done. No treatment will be given during the following menstrual cycle but the woman will be monitored. If conception occurs, the pregnancy will be followed in the same way as all other study pregnancies. If menses occurs, the woman may re-enter the trial during the subsequent cycle provided that the transvaginal U/S on cycle day 3 indicates both ovaries are < 10 cm (range 9-11 cm) on all diameters [or the absence of ovarian follicular cysts > 3 cm (range 2.7-3.3 cm)]. To prevent a repeat occurrence of hyperstimulation, subsequent treatment cycles should be conducted using a "step-down" administration of hMG, as follows: 3 amps of hMG for 2 days, then 1 amp daily.

After a rest cycle taken for personal reasons rather than a clinical indication, a woman may re-enter treatment only if menses occurs.

2. Spontaneous ovulation monitoring protocol

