Few, if any, measurable adverse effects are expected from either ICI or IUI. Patients will be asked to call the Research Nurse for temperature elevations $> 100^{\circ}\text{F}$. In general, patients will be evaluated clinically to ascertain subclinical pelvic inflammatory disease (PID). Patients will be counseled regarding the possibility of PID in an insemination cycle, and will be given a specific set of guidelines concerning when to call the Research Nurse.

2. Method of Ovulation Induction

a) Subjective Evaluation

Each questionnaire will evaluate the level of satisfaction with the time required for monitoring treatment with hMG/hCG, and the degree of discomfort experienced with parenteral injections, with venipunctures, and with ultrasound exams. Each patient will be asked to indicate the presence or absence (and degree) of symptoms such as abdominal pain

or discomfort, abdominal distension, bloating, weight gain, nausea, vomiting, diarrhea, headache, pain at injection sites, etc.

Patients who drop out of treatment will be asked to complete a questionnaire asking them to indicate and rank those factors that played a role in their decision. The list of factors include cost, time/inconvenience, requirement for parenteral medication, requirement for repeated venipuncture, requirement for ultrasounds, and concern regarding side effects (multiple gestation, hyperstimulation syndrome).

b) Objective Evaluation

1) All patients

Within 12 to 14 days after insemination, clinical criteria will be used to ascertain those patients with greater than mild hyperstimulation. Each woman will be asked whether she has experienced a weight gain of more than 10 pounds. Those reporting weight gain will be evaluated for evidence of severe hyperstimulation. The following laboratory measures and clinical criteria will be considered:

a) Ovaries > 10 cm in maximum diameter

b) Evidence of marked hemoconcentration:

1. Significant rise in hemoglobin or hematocrit > 15%
2. Evidence of electrolyte imbalance
3. Evidence of ascites or pleural effusion
4. Evidence of hypervolemic shock
5. Evidence of hypercoagulable state
6. Decreased urine output

The number of patients (cycles) requiring such workups, and the number meeting criteria for severe hyperstimulation, will be recorded. Most patients will not require such testing; in asymptomatic subjects no special effort will be made to evaluate ovarian size or to measure hematologic parameters following the hCG injection.

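### Step-down dosing is tied only to over-response before hCG; for severe hyperstimulation found after hCG, the text at hand states no dose reduction, and the written next dose is 2 or 4 amps per day

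*Protocol*

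**What the plan says.** **Before hCG.** Section 3.C.1 sets an over-response rule. If more than 6 follicles of at least 18 mm are seen, or estradiol reaches 3,000 pg/ml, "no hCG will be given and no insemination will be done". The next menstrual cycle is untreated. After menses, "the woman may re-enter the trial during the subsequent cycle provided that the transvaginal U/S on cycle day 3 indicates both ovaries are" below 10 cm in every diameter, or follicular cysts above 3 cm are absent. Then comes the dose rule: "To prevent a repeat occurrence of hyperstimulation, subsequent treatment cycles should be conducted using a" step-down schedule of 3 amps for two days and 1 amp daily after that. The footnotes to the decision charts repeat the same trigger.

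**After hCG.** Section 5.B.2.b provides a later check: "Within 12 to 14 days after insemination, clinical criteria will be used to ascertain those patients with greater than mild hyperstimulation". Women who report a gain of more than 10 pounds are evaluated for the severe form. The measures listed for consideration include "Ovaries > 10 cm in maximum diameter" and signs of hemoconcentration. The paragraph ends: "The number of patients (cycles) requiring such workups, and the number meeting criteria for severe hyperstimulation, will be recorded".

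**Next-cycle dose.** Section 3.C.1 starts hMG at 2 amps per day. The surviving labels of the cycle-2 chart, printed under the Figure 2 title, send a woman with two or more follicles in cycle 1 through the cycle 1 protocol again. A woman with only one follicle of at least 18 mm by day 15 receives hCG and "will commence the next cycle (unless pregnancy occurs) with 4 amps per day of hMG".

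**Latitude.** Section 3.C.1 allows a 10% margin on the estradiol and follicle-size criteria and asks for strict adherence to everything else. The only dose discretion it gives the investigator is upward, to at most 4 amps. Section 2 allows rest cycles on clinical grounds.

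**The concern.** The protocol gives the purpose of step-down as preventing a second episode of hyperstimulation. It assigns that protection to a woman whose cycle was cancelled before hCG. It does not assign it to a woman who went on to hCG and then developed the severe form. If she does not conceive and continues, the written dose for her next cycle is the one that preceded the event or, after a one-follicle cycle, a higher one.

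The cancellation limits still apply in her next cycle, but she passed them in the cycle that led to the event. Participant safety and uniform handling across the RMUs are at stake. Randomization, the endpoint and the primary comparison are not affected.

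**Working it through.** There is no plan figure to reproduce. The check has two parts.

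**1. Can the over-response rule reach a post-hCG event?**

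- Section 3.C.1: the trigger leads to no hCG and no insemination in that cycle.
- Section 5.B.2.b: the check is made 12 to 14 days after insemination.
- One cycle therefore cannot meet both. A woman picked up by the later check did not trigger the rule in that cycle. She is on step-down only if an over-response in an earlier cycle put her there.
- The re-entry remark that begins "After a rest cycle taken for personal reasons rather than a clinical indication" can be read to imply that the day-3 limit governs every clinical rest. Even on that reading only timing and re-entry are covered, not dose.

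**2. What does the dose difference amount to?**

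Inputs, all from Section 3.C.1: standard start 2 amps/day; increased start 4 amps/day; step-down 3 amps for 2 days, then 1 amp/day. The number of stimulation days, n, is an assumption. The protocol equates cycle day 15 with 12 days of stimulation.

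- Standard total: 2n
- Step-down total for n of 2 or more: 3 × 2 + 1 × (n − 2) = n + 4 (3 amps at n = 1)

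| Days | 2 amps/day | Step-down | Ratio, standard to step-down |
|---|---|---|---|
| 1 | 2 | 3 | 0.67 |
| 2 | 4 | 6 | 0.67 |
| 3 | 6 | 7 | 0.86 |
| 4 | 8 | 8 | 1.00 |
| 5 | 10 | 9 | 1.11 |
| 6 | 12 | 10 | 1.20 |
| 8 | 16 | 12 | 1.33 |
| 10 | 20 | 14 | 1.43 |
| 12 | 24 | 16 | 1.50 |

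Step-down starts higher, draws level at day 4 and is lower from day 5. The saving is 1 − 14/20 = 30% at 10 days and 1 − 16/24 = 33% at 12 days. The 12-day row is the slow-responder end. From the third stimulation day the daily dose is 1 amp against 2.

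After a one-follicle cycle the written dose is 4n: 40 amps against 14 at 10 days.

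No case count can be derived, because the documents state no rate of severe hyperstimulation.

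**The case against.** The strongest reply is that this is a claim of absence made without sight of some places where a rule could stand. One Section 5 figure is not shown, and the cycle-2 chart survives only as labels. The procedures manual and the adverse-reaction scenarios named in Appendix B are not at hand. This stands, and it limits the point to the text available. Neither part of Appendix B states a dose rule.

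A reader might infer that an RMU has only two options: deviate by giving step-down, or comply by repeating the dose. The documents do not support that. Section 2 permits a rest on clinical grounds, Table 3 provides withdrawal and final-disposition forms, and Section 9.E keeps withdrawn couples in the analysis. Nothing compels re-treatment. The step-down sentence is also advisory and states its purpose, so a physician could reasonably extend it. What remains is that none of these routes states a dose if she is treated again.

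A reader might also infer that step-down simply means less drug, or that a known number of women would be harmed. Neither follows. Step-down gives more drug on the first three days, amps are not a measure of harm, and the documents show no effect of step-down on risk after hCG. The affected group is narrow: she passed the cancellation limits, developed the severe form, did not conceive and continued.

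Two cautions about a remedy also stand. Section 5.B.2.b lists measures to be considered without saying which combination defines severe, so it cannot serve as an automatic trigger. Stopping hMG is as defensible as re-treating at a changed dose.

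**Conclusion.** The point holds in a limited form. In the text available, the skipped cycle, the day-3 limit and step-down in Section 3.C.1 follow only an over-response before hCG. Severe hyperstimulation found after hCG has a work-up and a count, but no stated dose reduction. The written default for the next cycle is 2 amps/day after two or more follicles or 4 amps/day after one, which works against the protocol's own aim of avoiding a repeat.

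Against 2 amps/day the planned difference is nil at 4 days and 6 amps at 10 days (20 against 14), with more drug under step-down on days 1 to 3. This rests on an assumed stimulation length and on no rule standing in the figure or manual not seen. The event is expected to be rare and its rate is not given. This is a safety gap in a dosing rule that should be closed. It is not a statistical error and does not threaten the trial's conclusions.

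**What to change.** Add to the over-response paragraph of Section 3.C.1:

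> The same applies to a woman whom the RMU physician records on the EHS form as having severe hyperstimulation after hCG: no treatment in the following menstrual cycle; re-entry after menses only if the day-3 ultrasound meets the limit above; and, if the physician judges further hMG safe, the step-down regimen instead of repeating 2 amps/day or rising to 4 amps/day; otherwise hMG is stopped and the couple stays in the intention-to-treat analysis.

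Cross-reference this in Section 5.B.2.b and as a branch on the cycle-2 chart. If step-down is to carry an exemption from the automatic increase to 4 amps, or from the two-consecutive-cycle treatment-failure exit in Figure 1, grant it to all women on step-down and not to this subgroup alone. That would fit Section 3.B, which ties the exit to poor response to rising doses.

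Cost: one added sentence and two cross-references. The severe-hyperstimulation (EHS) and rest-cycle (RC) forms are already in Table 3, and a baseline scan by day 3 is already required. Under Appendix C, decision 8, only cycles begun as study cycles count toward the four, so the skipped cycle uses none; a low-response step-down cycle still counts. The downside is a one-cycle delay and a possibly lower chance of conception for a few women, together with the higher dose on the first two days of step-down.

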Women who are not randomized to hMG stimulation will undergo insemination (IUI or ICI) timed to their spontaneous ovulation. The day of expected ovulation will be determined by averaging the length of previous menstrual cycles and/or by charts of basal body temperature. Beginning four days prior to expected ovulation, a woman will test for an LH surge using an OvuQuick (Quidel Inc) urinary dipstick. This urinary LH test will be performed daily, using the second void of the morning, until an LH surge is detected. Beginning two days prior to expected ovulation, couples will be instructed to abstain from vaginal intercourse and the male will be instructed not to ejaculate until the insemination sample is obtained. Insemination (IUI or ICI) will be performed on the day after the LH surge, between 9:00 a.m. and 3:00 p.m. If an LH surge is not detected, the woman should stop testing after 9 days. On cycle day 24 (range: days 22-26), a serum progesterone level should be obtained to determine whether she has ovulated. A women must exit the study if she has 2 documented anovulatory cycles.

3. IUI protocol

Washed sperm will be prepared using the following procedures. Semen specimens will be collected at the clinical site by masturbation after at least 48 hours of abstinence, and will be allowed to liquify at room temperature. Evaluation and preparation of the semen will begin within one hour of collection. A 0.07 ml aliquot of the semen will be analyzed for sperm concentration, percent motility and progression; slides will be made for sperm morphology assessment and video recordings will be made for subsequent CASA. Viscous samples will be mechanically dispensed by repeating passage through a sterile 15 gauge hypodermic needle attached to a sterile hypodermic syringe. The remaining semen will be transferred to a 15 ml Falcon conical tube. If the semen volume is greater than 5 ml, the sample will be divided equally between two 15 ml tubes. The semen will be diluted 1:2 (V/V) with medium. The

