 - a. Patients with minimal or mild endometriosis (AFS Stage I or II) are eligible after a 6-month interval post-treatment.
 - b. Patients with potentially significant defects seen on hysterosalpingogram (HSG) must be evaluated by repeat HSG and/or hysteroscopy. They are eligible if repeat HSG or hysteroscopy fails to confirm clinically significant abnormalities.
 - c. Patients with a bicornuate, arcuate, didelphic or T-shaped uterus are eligible.
 - d. Patients who have minor intra-abdominal adhesions that would not compromise fertility, and those who have had previous cervical conization or excision of uterine polyps, are eligible.
4. Late luteal phase biopsy normal (i.e. \pm 3 days of expected dating based on next menses). Outside biopsy results acceptable if RMU confirms diagnosis on review of slides.
5. Serum antisperm antibody test negative (< 50% of antibodies directed at the head and/or entire sperm by immunobead test on serum at 1:10 dilution); borderline results can be sent to U.C. Davis for review.
6. The following serum hormone concentrations are within the normal range of the RMU laboratory:
 - a. prolactin
 - b. thyroid stimulating hormone
 - c. follicle stimulating hormone (cycle day 1-5) [N.B. An extra tube of blood is to be drawn at the same time and sent to the DCC for quality control analyses.]
7. Two of the last 3 menstrual cycles between 24 and 40 days.
8. 1 year of unprotected intercourse in a stable monogamous relationship without a pregnancy.

Inclusion Criteria For Males

1. Age 55 years or younger.
2. Semen antisperm antibody test negative (< 20% of antibodies directed at the head and/or entire sperm by immunobead test on seminal sperm); borderline results can be sent to U.C. Davis for review.
3. Any motile sperm in the screening semen sample. (If < 2 million sperm/ml or < 10% motile sperm, special protocols will be used for semen evaluation.)
4. 1 year of unprotected intercourse in a stable monogamous relationship without a pregnancy.

Exclusion Criteria For Females

1. Previous IVF, GIFT, ZIFT or TET (ovulation induction).
2. Previous treatment with hMG.
3. Previous intrauterine insemination with the current partner.
4. History of chronic disease:
 - a. thyroid disease
 - b. diabetes
 - c. collagen vascular disease
 - d. chronic renal disease
 - e. chronic adrenal disease
 - f. any current chronic medication (previous 6 months or longer) for psychiatric indication

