All subjects will be asked to sign an informed consent to participate in the study (see Appendix A). Only those eligible couples who are willing to accept randomization can be enrolled in the trial.

The randomization procedure will stratify on RMU, i.e., each RMU will have its own independent randomization schedule. Permuted blocks of size four or eight will be employed within each RMU.

The DCC will review the relevant enrollment forms and will respond to the RMU with a decision on eligibility and, where appropriate, a randomization assignment. If the forms are incomplete or the documentation inadequate, the RMU will be notified; members of the DCC will meet weekly to review and resolve all such questionable cases. As part of quality assurance, the DCC will double check, in detail, on eligibility information for a randomly selected 4% of subjects, by requesting the entire medical record for review.

Section 5. MEASURES OF EFFICACY AND ADVERSE EFFECTS

[figure not shown]
A. Specific Measures of Efficacy

The relevant measure of treatment efficacy for this study is pregnancy, which will be determined by a standard protocol as outlined in Figure 2 below.

Ovulation will be taken to be the day of insemination, i.e., the day after a morning LH surge for women in the spontaneous ovulation groups, and the day corresponding to 36 hours after administration of hCG in the hMG-stimulated groups.

If menses does not occur by luteal day 14 (around cycle day 28-29), a blood sample will be drawn on luteal day 15 for serum β -hCG and the test will be repeated in two days (irrespective of whether menses begins in the interim) to evaluate whether β -hCG is rising (Romero et al., 1986). If the β -hCG is rising and if menses have not occurred, β -hCG will be repeated on luteal day 21 and a transvaginal ultrasound will be performed. This corresponds to the day that a gestational sac can usually first be seen by transvaginal ultrasound (Fossum et al., 1988). If no sac is seen, the β -hCG and ultrasound will be repeated four days later. Vaginal bleeding that occurs between the second β -hCG assay and the scheduled ultrasound will be evaluated by RMU physicians for possible miscarriage or ectopic pregnancy according to standard clinical practice.

Figure 2. Evaluation of Efficacy and Adverse Effects of Treatment

CYCLE 2

Two or more follicles on Cycle 1
Repeat Cycle 1 protocol

One follicle on Cycle 1
Increase hMG dose to 4-amps/day

No follicles on Cycle 1

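### In the no-hMG arms the progesterone sample is fixed at cycle days 22-26, so in usual cycles of about 37-40 days it precedes the end of LH testing and cannot show anovulation

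*Protocol*

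**What the plan says.** Protocol Section 3C.2 (spontaneous ovulation monitoring) governs the control and IUI arms.

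- **Expected ovulation** is individual. It comes from "averaging the length of previous menstrual cycles and/or by charts of basal body temperature".
- **LH testing** follows it: "Beginning four days prior to expected ovulation, a woman will test for an LH surge". It is done daily. "If an LH surge is not detected, the woman should stop testing after 9 days".
- **The ovulation check** is fixed for everyone: "On cycle day 24 (range: days 22-26), a serum progesterone level should be obtained to determine whether she has ovulated".
- **The exit rule**: "A women must exit the study if she has 2 documented anovulatory cycles".

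Section 3E, female inclusion item 7, admits long cycles: "Two of the last 3 menstrual cycles between 24 and 40 days". Item 4 of the same list judges the entry luteal biopsy within three "days of expected dating based on next menses", so there the plan dates a luteal event from the woman's own cycle. Section 5A takes ovulation to be "the day after a morning LH surge for women in the spontaneous ovulation groups", so a detected surge settles the matter. Section 9E counts a couple as a success only if the woman conceives while in the study. Appendix C, item 8, counts every started cycle towards the four.

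**The concern.** Two clocks run in the same cycle. The LH window moves later as the woman's cycle lengthens; the progesterone day does not. In a long enough cycle the sample that is meant to decide whether she ovulated is taken while the protocol still has her testing for the surge. A low value at that point is what an ovulatory woman with long cycles would be expected to show.

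This matters only when no surge is detected, because that is when progesterone is the sole test the section names. If such values are accepted as documentation, a woman whose surge is missed twice could be made to leave. She would lose her remaining cycles and count as a failure unless she had already conceived. This can happen only in the two arms without hMG.

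**Working it through.** **Luteal length.** Section 5A places luteal day 14 at about cycle day 28-29. Ovulation on day 14-15 plus 14 gives 28-29, so the protocol's calendar is reproduced. Section 3C.1 agrees: two days before expected ovulation is about day 12, hence ovulation about day 14. Carrying 14 days over to longer cycles is an assumption, varied below.

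**Formulas**, for usual cycle length L:
- expected ovulation = L - 14
- first LH test = L - 14 - 4 = L - 18
- ninth and last LH test = L - 18 + 8 = L - 10
- permitted draw = days 22-26

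| L | Expected ovulation | LH tests | Permitted draw days on or after last test | Draw relative to expected ovulation |
|---|---|---|---|---|
| 28 | 14 | 10-18 | 22-26 | +8 to +12 |
| 35 | 21 | 17-25 | 25-26 | +1 to +5 |
| 36 | 22 | 18-26 | 26 | 0 to +4 |
| 37 | 23 | 19-27 | none | -1 to +3 |
| 38 | 24 | 20-28 | none | -2 to +2 |
| 39 | 25 | 21-29 | none | -3 to +1 |
| 40 | 26 | 22-30 | none | -4 to 0 |

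The nominal day 24 precedes the last test from L = 35; the whole permitted range does so from L = 37.

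**Sensitivity.** The shortest cycle in which no permitted day reaches the last test is 35, 36, 37, 38 or 39 days for a luteal phase of 12, 13, 14, 15 or 16 days. Cycles of 39-40 days are affected throughout. If testing is read as ending one day later, each bound drops by one day.

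**Size in the control arm.** The protocol gives no cycle-length distribution and no missed-surge rate. Assume that a share q of control couples have ovulatory 37-40-day cycles, that the surge is missed with probability m per cycle independently, that every such draw is low and counts as documentation, and that lost cycles carry the average success rate.

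- Per-cycle rate from the hypothesised 0.075 over four cycles: 1 - 0.925^(1/4) = 0.0193. Cumulative: 0.0382 after two cycles, 0.0568 after three.
- Exit after cycle 2: probability m², loss 0.075 - 0.0382 = 0.0368.
- Exit after cycle 3: probability 2m²(1 - m), loss 0.075 - 0.0568 = 0.0182.
- A second label in cycle 4 loses nothing.
- Share losing cycles = q[m² + 2m²(1 - m)].
- Fall in control rate = q[0.0368m² + 0.0182 × 2m²(1 - m)].

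| q | m | Share losing cycles | Fall in control rate (percentage points) |
|---|---|---|---|
| 2% | 10% | 0.056% | 0.0014 |
| 5% | 20% | 0.52% | 0.013 |
| 10% | 30% | 2.16% | 0.056 |
| 10% | 50% | 5.0% | 0.14 |

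Even if 10% of control couples lost cycles 3 and 4, the fall would be 0.1 × 0.0368 = 0.37 points. The planned difference is 0.1875 - 0.075 = 11.25 points.

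**The case against.** The strongest objection is that the text does not say that two low progesterone values force exit. Exit follows documented anovulatory cycles, and the protocol gives neither a threshold nor a definition. A clinician who scheduled LH tests on days 22-30 is not told to treat a low day-24 value as proof, and Appendix B refers day-to-day detail to a procedures manual that is not shown. This stands, and it limits the point: wrongful exit follows on the natural reading, not by explicit rule. It does not remove the point. The sample is the only means Section 3C.2 names, nothing in the protocol or Appendix C retimes it, and Appendix B 2.4 has forms checked by computer against the protocol's timing, so a sensible later draw would fall outside the stated range.

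Second, the affected group is narrow: long ovulatory cycles, a surge missed in two cycles, and a low value both times. At 37 days a day-26 draw is three days past expected ovulation, so a low value is less certain there. Expected ovulation may also be set from temperature charts. All of this stands, and it is why the effect is small. The calculation also overstates the loss in one respect: women whose surges are missed would often have no insemination in their remaining cycles.

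Third, Section 4C offers couples in the no-hMG arms up to four hMG cycles at the end of the trial if they have not conceived. That may soften the loss to the couple, though the text does not say whether those made to exit qualify.

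A reader might infer that a day 22-26 value could also overturn a detected surge. The protocol does not support this: Section 5A takes the day after the surge as ovulation, and nothing lets a low value override it.

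**Conclusion.** The point holds in limited form. For usual cycles of 37-40 days, assuming a 14-day luteal phase, every permitted draw precedes the last LH test, so with no surge detected a low value cannot show anovulation. The lower bound moves to 35-39 days for luteal phases of 12-16 days. Whether two such cycles remove an ovulatory woman depends on how the undefined term is applied.

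A reader might infer that this biases the primary comparisons to a degree that matters. The documents do not support that. IUI versus ICI without hMG has the same rule in both arms, and hMG/IUI versus hMG/ICI is untouched. The other three comparisons could shift slightly in favour of hMG. For the control rate the assumed range is 0.001-0.056 percentage points, or 0.14 at the extreme, against 11.25 planned. The values of q and m are assumptions, so the true size is unknown but probably negligible. The change is optional; its benefit is a valid ovulation label and fewer wrongful exits in the no-hMG arms.

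**What to change.** Amend Section 3C.2 in two sentences.

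1. Keep day 24 (22-26) as the rule. When no surge is detected and that day would fall before the woman's last scheduled LH test (about 35 days or longer), draw the same single sample about 7 days after her own expected ovulation, and not before LH testing ends. With a 14-day luteal phase this is day L - 7: days 28 and 29 for 35- and 36-day cycles, and days 30-33 for 37-40-day cycles, each three days after the last test. The exact offset is for the investigators to set.
2. State that a cycle counts as documented anovulatory only if no surge was detected and progesterone was low on a sample taken after LH testing had ended.

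The retiming should be confined to long cycles. Applied to every no-surge cycle, it would move the draw in a 28-day cycle from day 24 to day 21. That is three days after the last LH test on day 18 where the present rule gives six, and so gives less protection if ovulation came late.

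The cost is a draw day that varies for women with long cycles, a small scheduling burden. No extra sample or test is needed.
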